5.2.3 Dose modification

Dose modification is not permitted and must be given as per randomisation.

5.2.4 Storage, preparation, dispensing and administration of trial drug

All study vaccines will be stored at the vaccination clinic at RCH and will be stored in accordance with the manufacturers' recommendations. See below:

- The Pfizer BioNTech vaccine should be stored at -70°C +/- 10°C and has a shelf life of 6 months. Once thawed, the vaccine may be stored for 31 days at 2-8°C. Once thawed vaccines will be stored in the RCH vaccination clinic refrigerators.
- The Moderna vaccine can be stored for 7 months at -25°C to -15°C. It should not be stored or transported on dry ice or below -40°C. Once thawed it should not be re-frozen and may be stored refrigerated at 2 °C to 8 °C protected from light for up to 30 days if not used (needle punctured). Chemical and physical stability of an unopened vial after removal from refrigerated conditions has been demonstrated for 12 hours at 8° to 25°C. Chemical and physical in-use stability has been demonstrated for 6 hours at 2 to 25 °C after first puncture. It should not be re-frozen once thawed.

Vaccine accountability, storage, shipment, and handling will be in accordance with relevant SOPs and forms.

5.2.5 Product accountability

The trial vaccines will be stored in the Immunisation clinic at RCH. Vaccination nurses trained in administering COVID-19 vaccines, will draw up the study vaccines each day and deliver them to the vaccination room. The study nurses will ensure that storage requirements are maintained. Study vaccines will be administered by unblinded vaccinators, who will maintain blinding such that those evaluating reactogenicity are kept blinded during the first month (28 days) post-vaccination.

The Immunisation clinic will maintain accurate records of the receipt of all trial vaccines, including dates of receipt. In addition, study nurses will keep accurate records regarding when and how much trial vaccine is dispensed and used for each participant in the trial. Reasons for departure from the expected dispensing regimen will be recorded. At the end of the trial, there will be final reconciliation of trial vaccine received, dispensed, consumed, and returned. Any discrepancies will be investigated, resolved, and documented by the trial team. Unused trial vaccines will be destroyed in compliance with applicable regulations.

Detailed information regarding product accountability will be provided in an SOP.

5.2.6 Excluded medications and treatments

There are no excluded medications or treatments apart from those associated with exclusions listed in section 4.4.2.

5.2.7 Concomitant therapy

Concomitant medications taken by participants during the study will be documented as part of the safety review procedures.

5.2.8 Discontinuation from trial intervention

See Section 7.5.

6 RANDOMISATION AND BLINDING

Once consent has been obtained, and following eligibility assessment, eligible participants will be recruited and randomised. Participants will be randomised 1:1:1:1 to one of the 4 intervention groups (*Comirnaty*[®] standard full dose, *Comirnaty*[®] fractional dose, *Spikevax*[®] standard half dose, *Spikevax*[®] fractional dose) stratified by the primary vaccine received (*Comirnaty*[®] or *Vaxzevria*[®]) and age (<50 and ≥50 years). A secure, password-protected web-based randomisation schedule will be provided by an independent statistician from the Melbourne Children's Trial Centre at the Murdoch Children's Research Institute. Blocked randomisation will be used with random blocks of permuted length. To ensure there are even numbers by primary vaccine and age group, participants will be recruited until the number required in each stratum has been reached.

40% of participants from each group will be included in the CMI subgroup analysis. The strata that will be used for CMI analysis will be identified at this time, and measures will be taken to ensure that the age strata (<50 and ≥50 years) are equally represented in this group. Only 10 CMI samples can be processed per day. We will therefore recruit the first 10 participants (5 in each of the age strata) who consent to participate in this substudy per day. Daily recruitment will be stopped once each subset is complete.

6.1 Concealment mechanism

Randomisation will be stratified according to age (<50 and ≥50 years) and primary vaccine (*Comirnaty*[®] or *Vaxzevria*[®]). Using REDCap the participants will be randomised to one of four groups in a 1:1:1:1 allocation ratio. (see table below).

Study staff involved in administering the vaccine will use REDCap to receive the information on the participant's randomisation number and vaccine allocation so they will be aware of which vaccine the participant is receiving. The participants themselves will remain blinded to their vaccine allocation (until day 28 post vaccination). Study staff involved in assessing reactogenicity will be blinded to each participant's vaccine allocation until 28 days post vaccination, as this variable will be hidden in REDCap for blinded study staff. Study staff involved in assessing immunogenicity outcomes will remain blinded during the analysis of specimens.

Vaccines will be prepared out of sight of the participant and the blind will be maintained by applying masking tape over the vaccine syringe, so the study participant can't see the volume.

The four booster vaccines will be prepared daily by the RCH immunisation clinic and delivered to the vaccination room and stored in the vaccine fridge. Only the study staff responsible for randomisation and drawing up and checking the vaccine will be aware of which vaccine is given to each study participant.

Primary vaccine	Age	Booster vaccine	Dose given
Pfizer-BioNTech	Below 50	Pfizer-BioNTech	30µg
		Pfizer-BioNTech	15µg
		Moderna	50µg
		Moderna	20 µg
	Above 50	Pfizer-BioNTech	30µg
		Pfizer-BioNTech	15µg
		Moderna	50µg
		Moderna	20 µg
AstraZeneca	Below 50	Pfizer-BioNTech	30µg
		Pfizer-BioNTech	15µg
		Moderna	50µg
		Moderna	20 µg
	Above 50	Pfizer-BioNTech	30µg
		Pfizer-BioNTech	15µg
		Moderna	50µg
		Moderna	20 µg

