TITLE	A randomised controlled trial to assess the immunogenicity, safety and reactogenicity of standard dose versus fractional doses of COVID-19 vaccines (Pfizer-BioNTech or Moderna) given as an additional dose after priming with Pfizer-BioNTech or AstraZeneca in healthy adults		
TRIAL DESCRIPTION	This clinical trial will be a single blind*, randomised study to determine the reactogenicity and immunogenicity of booster doses of SARS-CoV-2 vaccines in adults. Both fractional and standard doses will be tested.		
	Primary vaccine	Booster vaccines	
	Pfizer-BioNTech (BNT162b2)	1. Pfizer-BioNTech (BNT162b2 or Comirnaty ®) Standard dose (30µg) n=100	
		2. Pfizer-BioNTech (BNT162b2 or Comirnaty ®) Fractional dose (15µg) n=100	
		3. Moderna (mRNA-1273 or Spikevax ®) Standard Dose (50µg)** n=100	
		4. Moderna (mRNA-1273 or Spikevax ®) Fractional Dose (20µg)** n=100	
	AstraZeneca (ChAdOx1-S, or Vaxzevria ®)	5. Pfizer-BioNTech (BNT162b2 or Comirnaty ®) Standard Dose (30µg) n=100	
		6. Pfizer-BioNTech (BNT162b2 or Comirnaty ®) Fractional Dose (15µg) n=100	
		7. Moderna (mRNA-1273 or Spikevax ®) Standard Dose (50µg)** n=100	
8. Moderna (mRNA-1273 or Spikevax ®) Fractional Dose (20µg)** n=100			

* Subjects and assessors will be blinded to the vaccine allocation for one month (28 days) following administration, and laboratory staff will be blinded to vaccine allocation associated with specimens.
 
**Recent data from UK/USA indicate that reactogenicity is an issue for full dose Moderna (100µg) boosters, hence we are using fractional doses for this vaccine. Currently the recommended standard booster dose is 50µg.
			
OBJECTIVES	
Primary objectives –
 
 To assess and compare the immune response measured as binding antibodies (IgG ELISA) following standard versus fractional doses of Pfizer or Moderna vaccine given as single additional doses in adults 18 years or older in Australia who have been primed through previous vaccination with Pfizer or AstraZeneca vaccines. (Timepoint – 28 days post vaccination) 		

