4 TRIAL DESIGN

4.1 Overall design

This clinical trial will be a single blind, randomised study to determine the immunogenicity and reactogenicity of booster doses of SARS-CoV-2 vaccines in adults. Both fractional and standard doses will be tested.

The groups are described below. The trial intervention will be a single booster dose of vaccine: -

Primary vaccine	Booster vaccines
Pfizer-BioNTech (BNT162b2, or Comirnaty [®])	1. Pfizer-BioNTech (BNT162b2, or Comirnaty [®]) Standard dose
	2. Pfizer-BioNTech (BNT162b2, or Comirnaty [®]) Fractional dose
	3. Moderna (mRNA-1273, or Spikevax [®]) Standard Dose
	4. Moderna (mRNA-1273, or Spikevax [®]) Fractional Dose
AstraZeneca (ChAdOx1-S, or Vaxzevria [®])	5. Pfizer-BioNTech (BNT162b2, or Comirnaty [®]) Standard Dose
	6. Pfizer-BioNTech (BNT162b2, or Comirnaty [®]) Fractional Dose
	7. Moderna (mRNA-1273, or Spikevax [®]) Standard Dose
	8. Moderna (mRNA-1273, or Spikevax [®]) Fractional Dose

The trial intervention will be given 6-9 months after the primary vaccine. This is in line with ATAGI recommendations for booster vaccine doses which allows booster doses from 5 months onwards (2). The groups size will be 100 individuals with an even spread of participants above and below 50 years in each group. The trial will be single site.

The trial will be single blind. The participants and those evaluating reactogenicity will be blinded to the vaccine allocation for the first 28 days following vaccination. After that, both the clinical investigators and potentially participants will be aware of their investigational product allocation. Immunologists and laboratory staff will remain blinded to the investigational product allocation.

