6.2 Breaking of the trial blind

6.2.1 On trial

The study will be blinded for the first 28 days only. In the unlikely event that it becomes necessary to unblind during this period that decision will be taken by the PI, and the subject and physicians who may be caring for the subject will be made aware of the allocation.

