7 TRIAL VISITS AND PROCEDURES

7.1 Schedule of assessments

	Visit 1 (day 0)	Visit 2 (day 1)	Visit 3 (day 7)	Visit 4 (day 28)	Visit 5 (3 mths)	Visit 6 (6 mths)	Visit 7 (12 mths)
Timing	Day 0	Day 1	Day 7	Day 28	3 months	6 months	12 months
Visit window			+ 3 days	+ 7 days	+/- 14 days	+/- 14 days	+/- 14 days
Informed consent	X						
Eligibility confirmation	X						
Randomisation	X						

Blood sampling	X			X		X	X
Vaccination	X						
Vital signs	X						
Issue diary card, ruler and thermometer	X						
Collect diary card			X				
Documentation of Solicited AE	X	X	X				
Documentation of unsolicited AE	X	X	X	X			
Documentation of medically attended AE	X	X	X	X	X		
Documentation of SAE	Throughout study period						
Documentation of confirmed COVID-19 infection	Throughout study period						

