7.2.3 Visit 4 (Day 28)

An in-person visit will be conducted 28 days following vaccination. All Unsolicited Adverse Events will be documented. Study staff will also document any new information regarding solicited adverse events with onset up to 7 days following vaccination, such as resolution. The participant will be informed which vaccine they received based on entry into the CRF by an unblinded staff member.

For all participants, 5mL of blood will be collected in an SST tube. For participants in the CMI subset, 3mL of blood for Quantiferon test will be collected in a heparinised tube, and 20mL of blood for PBMC will be collected in a heparinised tube. Blood samples will be kept at room temperature and transferred to the laboratory within 3 hours of collection.

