8.2 Capturing and eliciting adverse event/reaction information

Participants will be asked to record local and systemic AEs for 7 days (and longer if symptoms persist at day seven, until resolution or stabilisation) following vaccination in the electronic or paper diary card (solicited AEs). Unsolicited AEs All local and systemic AEs occurring in the 28 days following vaccination observed by the Investigator or reported by the participant, whether or not attributed to study medication, will also be recorded in participant diary and CRF.

Serious adverse events (SAE's) will be followed up for the duration of the trial. Adverse events of special interest will be categorised as per CEPI guidelines (1).

Adverse reactions will be reported through the RCH immunisation service and escalated to the Victorian Specialist Immunisation Services.

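### The staff blind ends on calendar day 28, but Visit 4, where later unsolicited adverse events are recorded and judged, can run to day 35

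*Combined protocol and SAP*

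**What the plan says.** The end of the blind is set by elapsed time wherever the protocol states it as a rule:

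- Synopsis footnote: "Subjects and assessors will be blinded to the vaccine allocation for one month (28 days) following administration".
- Section 4.1, on the period after 28 days: "After that, both the clinical investigators and potentially participants will be aware of their investigational product allocation".
- Section 6.1, for staff assessing reactogenicity: "vaccine allocation until 28 days post vaccination, as this variable will be hidden in REDCap for blinded study staff".
- Section 6.2.1: "The study will be blinded for the first 28 days only".

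The schedule in 7.1 places Visit 4 at day 28 with a window of plus 7 days and no minus side. The row "Documentation of unsolicited AE" is marked at Visits 1, 2, 3 and 4. Section 7.2.3 says of Visit 4: "All Unsolicited Adverse Events will be documented". It also provides for updates on solicited events that began in the first week, and then states: "The participant will be informed which vaccine they received based on entry into the CRF by an unblinded staff member".

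Section 8.2 adds that unsolicited events in the 28 days, "whether or not attributed to study medication, will also be recorded in participant diary and CRF".

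**The concern.** The blind expires on the first day on which Visit 4 is allowed. Any in-window visit after that day falls in a period when, by section 4.1, clinical investigators know the allocation and, by 6.1, the REDCap field need no longer be hidden from assessors.

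The tasks at stake involve judgement. Relatedness (8.4) turns on timing, alternative causes and similarity to known vaccine reactions. The severity scale (8.5) turns on limitation of activity and need for intervention. The plan also carries a prior expectation: 2.3.2 and 4.2 present fewer reactions as an advantage of the fractional dose. An assessor who knows which dose or product was given may probe, grade or attribute an event differently.

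Two uses of the data depend on this. Safety, including 28-day unsolicited events, is a listed secondary outcome (3.2.2). And section 10.1.3 has the DSMB review serious events and events judged at least possibly related, so attribution helps decide what the board sees.

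**Working it through.** The plan states no figure on this point, so there is none to reproduce. The check is calendar arithmetic plus a comparison of sections.

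**1. Permitted days for Visit 4 (7.1).** Earliest day 28; latest 28 + 7 = 35. That is 8 permitted days. Counting day 28 itself as still blinded, which favours the plan, 7 of the 8 (7/8 = 87.5%) fall after the blind.

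**2. Participants affected.** Let p be the share of the 800 participants seen exactly on day 28, and assume that all attend within the window. The number assessed after the blind is 800 × (1 − p). The documents do not give p, so each row is an assumption:

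| p | Visit 4 after day 28 |
|---|---|
| 100% | 0 |
| 75% | 200 |
| 50% | 400 |
| 12.5% (visits spread evenly over the 8 days) | 700 |
| 0% | 800 |

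**3. How much of the reporting period rests on Visit 4.** The diary card is completed up to day 7 (7.2.1, Visit 1) and collected at Visit 3, whose window is day 7 to day 7 + 3 = 10. No later diary collection is scheduled, although 8.2 refers to diary recording over the 28 days. Visit 5 (7.2.4) takes only new information on unsolicited events, such as resolution, together with medically attended and serious events. So Visit 4 is the only scheduled contact for first documenting unsolicited events with onset after Visit 3:

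- Visit 3 on day 7: days 8 to 28, which is 21 of 28 days (75%).
- Visit 3 on day 10: days 11 to 28, which is 18 of 28 days (64%).

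**4. Whether the primary outcomes are touched.** The reactogenicity diary is reviewed by day 10 at the latest, inside the blind. Laboratory staff stay blinded under 4.1 and 6.1, so the 28-day IgG result is not exposed.

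**5. Who is covered.** The 6.1 sentence names only reactogenicity staff. The extension to those judging unsolicited events rests on the synopsis (assessors) and 4.1 (clinical investigators). No section sets a different end of blinding for them.

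**The case against.** The strongest reply is that 7.2.3 already gives the intended order. It places disclosure to the participant at Visit 4, lists it after adverse-event documentation, and has it come from an entry by an unblinded staff member, which suggests that the staff running the visit do not hold the allocation. Section 6.1 also says that only those who randomise and prepare the vaccine know it. On this view, 28 days is shorthand for Visit 4.

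Much of that stands for participants: no section describes telling them before Visit 4. It does not settle the position of assessors. The order in 7.2.3 is not made binding and concerns only what the participant is told, while 4.1 says that clinical investigators know after 28 days and 6.1 ties the hidden field to the calendar.

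A second reply is that unsolicited events are documented at four scheduled contacts, of which only Visit 4 can fall after day 28, so at most 1 in 4 contacts (25%) is exposed. The count is right, but contacts are a poor denominator, because Visit 4 alone covers 64% to 75% of the onset days.

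Three further points narrow the concern and stand:

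- Section 11.3 specifies no between-group test of unsolicited events, so no planned formal comparison is biased.
- The events themselves arise within 28 days, while the participant is blinded; only their late recording, grading and attribution are exposed.
- The synopsis has the DSMB review safety data monthly without limiting it to related events, so relatedness may not be the board's only filter.

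Open follow-up of medically attended events to 3 months and serious events to 12 months is a declared design choice and is not criticised here.

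**Conclusion.** The mismatch is real: followed literally, the plan lets staff who may know the allocation grade unsolicited events and judge their relatedness at Visit 4. It bears on a secondary safety outcome and on the related-event listing for the DSMB. It is a cheap improvement, not a threat to the primary results.

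A reader might infer that most Visit 4 assessments will be unblinded, because 7 of the 8 permitted days follow day 28. The documents do not support that. Section 7.2.3 schedules the visit at 28 days, the window is a tolerance, and no distribution of visit days is given. The supportable statement is some, and possibly most, with a range of 0 to 800 participants. Nor do the documents support an inference that the reactogenicity outcome is compromised, or that participants will routinely know their vaccine before being asked about events.

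Confidence is high that the rules do not fit together, and low on how many participants would be affected.

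**What to change.** In the synopsis footnote and sections 4.1, 6.1 and 6.2.1, replace the 28-day limit with a condition. Assessors and participants stay blinded until Visit 4 adverse-event documentation, severity and relatedness have been saved in REDCap or, if Visit 4 is missed, until its window closes at day 35. State that this covers everyone who grades or attributes unsolicited events, not only reactogenicity staff. Key the release of the hidden REDCap field to the same condition. In 7.2.3, make disclosure to the participant explicitly the last step of the visit.

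The day-35 fallback is needed because a rule tied only to the saved form would leave a participant who misses Visit 4 blinded with no end date. The emergency unblinding provision in 6.2.1 is unchanged in substance; its wording should span the whole blinded period.

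The cost is protocol wording and one REDCap setting. The downside is that some participants and staff learn the allocation up to 7 days later (35 − 28).

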6.2 Breaking of the trial blind

6.2.1 On trial

The study will be blinded for the first 28 days only. In the unlikely event that it becomes necessary to unblind during this period that decision will be taken by the PI, and the subject and physicians who may be caring for the subject will be made aware of the allocation.

7 TRIAL VISITS AND PROCEDURES

7.1 Schedule of assessments

	Visit 1 (day 0)	Visit 2 (day 1)	Visit 3 (day 7)	Visit 4 (day 28)	Visit 5 (3 mths)	Visit 6 (6 mths)	Visit 7 (12 mths)
Timing	Day 0	Day 1	Day 7	Day 28	3 months	6 months	12 months
Visit window			+ 3 days	+ 7 days	+/- 14 days	+/- 14 days	+/- 14 days
Informed consent	X						
Eligibility confirmation	X						
Randomisation	X						

Blood sampling	X			X		X	X
Vaccination	X						
Vital signs	X						
Issue diary card, ruler and thermometer	X						
Collect diary card			X				
Documentation of Solicited AE	X	X	X				
Documentation of unsolicited AE	X	X	X	X			
Documentation of medically attended AE	X	X	X	X	X		
Documentation of SAE	Throughout study period						
Documentation of confirmed COVID-19 infection	Throughout study period						

7.2 Description of procedures

7.2.1 Visit 1 (Day 0)

Informed consent must be signed by both participant and study doctor or nurse.

Participant eligibility must be confirmed prior to randomisation and on the same date as administration of the investigational product.

Eligibility must be confirmed by a study doctor or study nurse. Randomisation must be completed by the unblinded vaccinator who will document the participant's randomisation number on the enrolment log.

Study staff will administer a Visit 1 questionnaire documenting demographic information, height and weight, dates and type of primary COVID-19 vaccine, any comorbidities and concomitant medication.

The following vital signs will be recorded by a study doctor or study nurse prior to vaccination: temperature, pulse rate, respiratory rate, and blood pressure.

Prior to vaccination, for all participants, 5mL of blood will be collected and processed according to the SOP. CMI participants will have an additional 25ml collected and processed for Quantiferon analysis and PBMC separation and storage.

Following randomisation, the unblinded vaccinator will administer the applicable vaccine to the participant.

The following vital signs will be recorded by a study doctor or study nurse 15 minutes following vaccination: temperature, pulse rate, respiratory rate, and blood pressure.

Study staff will provide participant with reactogenicity diary card and instruct the participant on how to complete the diary card up to and including 7 days following vaccination.

Study staff will provide the participant with a thermometer and ruler and detailed instructions on how to use these for measuring temperature and potential erythema and induration. Study staff will provide the participant with a schedule of visit appointments and instruct the participant on how to contact the study staff in case of any SAE or symptoms suggestive of COVID-19.

Study staff will keep the participant under observation for minimum 15 minutes and document any immediate adverse events.

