3. TRIAL OBJECTIVES AND OUTCOMES

3.1 Objectives

3.1.1 Primary objective

- The primary objectives of the study are to: -To assess and compare the immune response measured as binding antibodies (IgG ELISA) following standard versus fractional doses of Pfizer or Moderna vaccine given as a single additional dose to adults 18 years or older in Australia who have been primed through previous vaccination with Pfizer or AstraZeneca vaccines. (Timepoint – 28 days post vaccination)
- To assess the rate and severity of reactogenicity within one-week post-booster for each schedule evaluated.

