4.4.1 Inclusion criteria

Each participant must meet all the following criteria to be enrolled in this trial:

1. Have completed two doses of Pfizer-BioNTech or AstraZeneca vaccines with the recommended schedule 6 months prior to the date of enrolment
2. Willing and able to give written informed consent
3. Aged 18 years or above
4. Willing to complete the follow-up requirements of the study

Note that subjects with comorbidities other than those listed below as contraindications will be included. Pregnant women or women who may become pregnant will be included.

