11.3 Methods of analysis

Reactogenicity following immunisations will be presented as the number and percentage of participants self-reporting local reactions (pain; tenderness, redness; swelling at or near the injection site) and systemic reactions (fever, nausea/vomiting, headache, fatigue/malaise, myalgia), and the severity of

these reactions (mild, moderate, severe, life-threatening or fatal). Reactogenicity data will be presented separately by group and time point.

For immunogenicity, antibody levels will be presented as geometric mean titres (GMT) with 95% confidence intervals. Changes from baseline will be expressed as geometric mean fold ratios (GMFR), calculated as the ratio of the post-booster GMT to the baseline GMT. Seroresponse will be defined as a ≥ 4 -fold rise in post-booster antibody levels compared to baseline (or ≥ 2 -fold rise if the baseline (pre-booster) antibody level was ≥ 200 BAU/ml). To assess the non-inferiority of the fractional dose compared with the standard dose, comparisons will be based on the difference in percentage of participants with seroresponse. Using a non-inferiority margin of -10% (fractional-dose minus standard dose), non-inferiority will be declared if the lower limit of the 95% confidence interval around the difference in percentages is greater than -10%, where confidence intervals are calculated using Score-based methods (14)

Analyses will be performed using Stata software (15). Detailed methodology will be outlined in a separate Statistical Analysis Plan.

Primary outcome (All samples at all timepoints)

The binding IgG data using the Euroimmun S1 IgG ELISA kits will be reported as relative units/ml (RU/ml) as per manufacturer's instructions. A result of < 8 RU/ml: negative (IgG Antibodies for SARS-CoV-2 are not detected), ≥ 8 to < 11 RU/ml: borderline (IgG antibodies is indeterminate/equivocal with this sample), ≥ 11 RU/ml: positive (IgG antibodies for SARS-CoV-2 are detected). Conversion to binding antibody units (BAU/ml) will also be done using the WHO reference serum from NIBSC, UK. Data will be presented as geometric mean titres and 95% confidence intervals.

Analysis comparing fractional and standard dose groups will be based on seroresponse rate (SRR) at 28 days post study vaccine, defined as:

- ≥ 4 -fold rise in GMCs at 28 days post study vaccine from baseline among subjects with no pre-dose (< 200 BAU/ml) detectable titres

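### Apart from temperature, no systemic symptom is recorded before the injection and no rule covers symptoms already present, so the reaction rates in a primary outcome can include background symptoms.

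*Combined protocol and SAP*

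**What the plan says.** The second primary objective in section 3.1.1 is "To assess the rate and severity of reactogenicity within one-week post-booster for each schedule evaluated". It asks for a rate for each schedule, not only for a contrast between doses.

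Section 7.2.1, Visit 1 (Day 0), sets out what is collected before the injection. Staff take blood and measure vital signs: "The following vital signs will be recorded by a study doctor or study nurse prior to vaccination". The four signs listed are temperature, pulse, breathing rate and blood pressure. A questionnaire covers demographics, height and weight, and "dates and type of primary COVID-19 vaccine, any comorbidities and concomitant medication". No item asks about symptoms present that day.

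Symptom recording begins after the injection. Staff are to "instruct the participant on how to complete the diary card up to and including 7 days following vaccination", and section 8.2 says "Participants will be asked to record local and systemic AEs for 7 days".

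Section 11.3 summarises reactogenicity as "the number and percentage of participants self-reporting local reactions", together with the systemic reactions and their severity, by group and time point. It mentions no comparison with the participant's state before the dose. Its systemic list is fever, nausea/vomiting, headache, fatigue/malaise and myalgia. Table 1 in section 3.2.1 has these and arthralgia as well.

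Section 4.4.1 notes that "subjects with comorbidities other than those listed below as contraindications will be included". Section 4.3 sets no upper age limit, and section 4.1 plans an even split above and below 50 years.

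**The concern.** Headache, tiredness and aches are common complaints that can be present on any given day, and the trial admits older adults and people with comorbidities. Table 1 grades fatigue, myalgia and arthralgia by how far they interfere with activity, not by change from the participant's usual state. A long-standing symptom entered on the diary therefore looks the same as a reaction to the booster.

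Because the objective is an absolute rate for each schedule, balance between the arms does not remove this background from the reported figures. It also narrows any difference seen between standard and fractional doses, and section 4.2 gives fewer moderate reactions as an advantage of the fractional dose. A symptom grade from before the dose cannot be collected reliably afterwards, so a later analysis could not repair the gap.

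**Working it through.** **The plan's own precision figure.** Section 11.1 assumes a 50% reaction rate and 100 participants. At the 95% level (assumed, since section 11.1 does not state it) the half-width is 1.96 × √(0.5 × 0.5 / 100) = 1.96 × 0.05 = 0.098. The stated 9.8 percentage points reproduce.

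**Is there a baseline for each systemic item?**
- Fever: yes, through the temperature taken before vaccination.
- Nausea/vomiting, headache, fatigue/malaise, myalgia, arthralgia: none is described.
- The schedule in section 7.1 marks solicited AEs on Day 0, but the Visit 1 text describes only immediate events during the observation period after the injection.
- Comorbidities and medication are recorded, but they do not show whether a symptom is present that day or at what grade.

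**Illustration of size.** The documents give no background rate, so these inputs are assumptions:
- b is the share with the symptom at injection in whom it continues into the 7 days, taken as 5% to 20%.
- r is the vaccine-caused rate, taken as independent of b.

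Reported any-symptom rate = b + (1 − b) × r. The excess is b × (1 − r). A difference between two doses is multiplied by (1 − b).

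| b | reported, r = 50% | reported, r = 40% | difference (true 10 points) | reported, r = 20% |
|---|---|---|---|---|
| 5% | 52.5% | 43.0% | 9.5 | 24.0% |
| 10% | 55.0% | 46.0% | 9.0 | 28.0% |
| 20% | 60.0% | 52.0% | 8.0 | 36.0% |

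Example: 0.20 + 0.80 × 0.50 = 0.60. The excess reaches 9.8 points when b = 9.8/50 = 19.6% at r = 50%, or b = 9.8/80 = 12.25% at r = 20%. Less common reactions are affected more.

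**What a new-or-worse count would give.** Let q be the share of vaccine-caused symptoms, among those already symptomatic, that exceed the baseline grade. Then the rate is (1 − b) × r + b × r × q.
- If q = 1, the rate is r, the true value.
- If q = 0, it is (1 − b) × r. At b = 20% this is 0.80 × 50% = 40% and 0.80 × 40% = 32%. Both are too low, and the difference is still 8.0 points.

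So (1 − b) × r ≤ new-or-worse rate ≤ r ≤ any-symptom rate. For symptoms present at injection, the two counts enclose the vaccine-caused rate, and the enclosure is at most b wide (at b = 20%, r = 50%: 40% to 60%). Unrelated symptoms that start or worsen later in the week enter both counts and are not removed by either.

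**The case against.** The strongest case against has five parts.

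- **Section 11.3 does not say that pre-existing symptoms count.** A reader might infer that it does. It is only silent, and it leaves detail to a separate SAP. That SAP, the diary card and the SOPs are not in the documents, so a baseline item there cannot be ruled out. This stands. The supportable statement is that no rule is given, so such symptoms can be counted.
- **Other safeguards exist.** AE records carry onset date and relatedness (sections 8.3 and 8.4), staff review the diary on Day 7, and the synopsis has moderate and severe reactions reviewed. These help, but none supplies a grade from before the dose, and section 11.3 does not apply relatedness to reactogenicity.
- **No dose comparison is at risk.** It is tempting to read the gap as bias towards one dose. The documents do not support that: allocation is randomised within age and primary-vaccine strata, and section 11.3 plans descriptive reactogenicity tables with no test between doses. The only non-inferiority comparison is on seroresponse. What remains is the absolute rates and a descriptive dilution.
- **Counting new-or-worse symptoms does not cure the dilution.** Correct: the working shows that it can undercount and leave the difference just as small. It belongs beside the any-symptom table, not in place of it.
- **All post-dose symptoms is a recognised descriptive count.** Section 3.2.1 describes its method as accepted and standardised, and an any-symptom table helps comparison with other studies. This is a good reason to keep that table.

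Two broader readings also fail. It would be wrong to say that no Table 1 item has a baseline, because fever does. Nor can joint pain be said to enter the section 11.3 rates, because arthralgia is not in that list.

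**Conclusion.** The point holds as a gap in data collection and definition. It does not threaten the validity of the trial. Apart from temperature, the visible protocol records no Table 1 systemic symptom before the injection, and section 11.3 has no rule for symptoms already present. Background symptoms can therefore sit inside the per-group rates of a primary outcome.

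The size cannot be fixed from the documents. With an assumed 5% to 20% symptomatic at injection, independent of the vaccine effect, a 50% rate is overstated by up to 2.5 to 10 points. The top of that range is about equal to the plan's 9.8-point precision; lower values fall well short of it. These are upper limits, because they assume that every such symptom continues and is entered on the diary. A reader might apply the same arithmetic to all background symptoms over the week, but that would overstate what a Visit 1 record can identify.

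**What to change.** 1. In section 7.2.1, Visit 1, before vaccination, record each Table 1 systemic symptom and its grade on the same scale as the diary.
2. In section 11.3, keep the any-symptom table as the main presentation. Add a second table counting symptoms that are new or of higher grade than before the injection. State that the first can overcount and the second can undercount, so that together they bracket the vaccine-caused rate for symptoms present at injection. State also that unrelated symptoms starting later in the week remain in both.
3. Reconcile the systemic lists: arthralgia is in Table 1, the synopsis and section 9.1.1 but missing from section 11.3.
4. If the diary card or the separate SAP already holds a baseline item and a counting rule, it is enough to say so in sections 7.2.1 and 11.3.

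Cost: about one minute at Visit 1, one CRF block and a second table.
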